## 1. INTRODUCTION AND RATIONALE

Because of the increasing rates of morbid obesity and herewith increasing requests for bariatric surgery, the popularity of fast-track protocols is increasing. These Enhanced Recovery After Bariatric Surgery (ERABS) protocols often include short-term thromboprophylaxis and short length of hospital stay (LOS), with the aim to discharge patients on the first postoperative day(1, 2). Even though ERABS has many positive outcomes, it may also negatively affect the diagnosis of postoperative hemorrhage due to the short time window for diagnosing postoperative complications.

Most current literature states that postoperative hemorrhage occurs in 2.0% of patients undergoing laparoscopic sleeve gastrectomy (LSG) and in 1.5-3.1% of patients undergoing a laparoscopic Roux-en-Y gastric bypass (LRYGB)(3, 4). It is described that over the years, there seems to be an increase in the occurrence of postoperative hemorrhage, while the risk of venous thromboembolic events (VTE) is decreasing(5). In our center, overall postoperative hemorrhage rates of LRYGB and LSG have been stable since 2014, with more hemorrhage occurring after a LSG (2.2%) than after a LRYGB (1.3%). The rates of peroperative hemorrhage requiring hemostatic clips was 63.3% between January 2017 and March 2019. The rate of diagnosed VTE within 3 months postoperative is 0.05% since 2014 in this center.

Tranexamic acid (TA) is a plasminogen inhibitor that can be used to inhibit fibrinolysis during or after surgery and thus minimize the risk of developing perioperative hemorrhage. Little is known about the use of TA in bariatric surgery. Nevertheless, in several other surgical areas such as for coronary-artery surgery and arthroplasty, perioperative administration of TA has proven its value in preventing postoperative hemorrhage (6-8). Until now, the use of TA to prevent postoperative hemorrhage in bariatric surgery is once described by Hussain et al.(9). The authors performed a meta-analysis of administration of TA during laparoscopic sleeve gastrectomies and concluded that administration of TA is a simple yet effective way to lower the rates of staple line hemorrhage, while shortening the length of surgery. In the end of 2018, Klaassen et al described that reoperations may be prevented due to postoperative administration of TA in case of a suspicion of an already present hemorrhage(10).

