Because of the serious risks of postoperative hemorrhage, the need for preventive measures in bariatric fast-track surgery is increasing. This trial aims to investigate if peroperative administration of TA can reduce the postoperative hemorrhage rates in laparoscopic sleeve gastrectomy.

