#### **8.1.2 Secondary study parameters/endpoints (if applicable)**

Secondary outcome measures are the decrease in hemoglobin after the procedure at 1 day postoperative, rates of postoperative hemorrhage (i.e. hemorrhage needing administration of packed cells or a surgical or radiological re-intervention) within 30 days postoperative and rates of VTE within 3 months postoperative.

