### 10.1 Primary study parameter(s)

Differences in use of hemostatic staples (yes/no) between the 2 groups will be determined using Chi-Square tests. The difference in hemoglobin decrease will be tested using multivariate linear regression analysis, correcting for comorbidities (hypertension, diabetes, dyslipidemia) and use of hemostatic staples. These same analyses will be performed to assess the differences in amount of patients needing to undergo a re-

intervention, but adding administration of postoperative tranexamic acid as a covariate. Results will be evaluated at a significance threshold of  $p < 0.05$  (two-sided).

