### **10.2 Secondary study parameter(s)**

Differences in rates of DVT (yes/no), PE (yes/no) and in rates of administration of postoperative tranexamic acid (yes/no) between the 2 groups will be calculated using Chi-Square (Fisher's Exact) tests.

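### Section 10.1 assigns the haemoglobin linear regression, with post-randomisation covariates, to re-intervention, a yes/no outcome with about two expected events

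*Protocol*

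**What the plan says.** Section 10.1 gives the primary outcome, staple use (yes/no), a Chi-square test. For haemoglobin it states: "The difference in hemoglobin decrease will be tested using multivariate linear regression analysis", adjusted for hypertension, diabetes, dyslipidaemia and staple use. It continues: "These same analyses will be performed to assess the differences in amount of patients needing to undergo" a re-intervention, "but adding administration of postoperative tranexamic acid as a covariate". All results in that section are judged at a two-sided 5% threshold.

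Section 10.2 treats the other rare yes/no outcomes differently. Differences in DVT, PE and use of postoperative TA "between the 2 groups will be calculated using Chi-Square (Fisher's Exact) tests".

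Re-intervention is secondary. Section 2 lists reoperation for haemorrhage within 30 days among the secondary objectives. Section 8.1.2 includes re-intervention in postoperative haemorrhage, defined as "hemorrhage needing administration of packed cells or a surgical or radiological re-intervention) within 30 days postoperative". The Introduction gives the centre's postoperative haemorrhage rate after sleeve gastrectomy as 2.2% and the literature rate as 2.0%.

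**The concern.** A Chi-square test takes no covariate. A sentence that carries an analysis over and adds a covariate can therefore only mean the regression, and the only regression the protocol names is linear. Three things follow.

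- **Too few events.** The model has six terms (arm, three comorbidities, staple use, postoperative TA) for about two events. The fitted coefficients would mostly describe the covariate pattern of one or two patients.
- **Adjustment for consequences of treatment.** Staple use is the primary outcome, which TA is meant to change. Postoperative TA is itself compared between arms in Section 10.2, and the Introduction describes its use when a haemorrhage is already suspected. Conditioning on either can take out part of the effect being tested.
- **Inconsistency.** Re-intervention is as sparse and binary as DVT or PE, yet it does not get the test used for them.

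At stake is how a clinically important secondary result is reported. Its p-value would depend heavily on chance covariate patterns, and in some trials there would be no estimate at all.

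**Working it through.** **Inputs.** Haemorrhage rate after sleeve gastrectomy 2.2% (Introduction). Size 2 × 36 = 72 (Section 4.4) or 100, taken as 50 per arm (Section 3). Both sizes are carried through. The protocol gives no rate for re-intervention alone. Since Section 8.1.2 counts re-intervention within haemorrhage, 2.2% is used as an upper bound. A halved rate of 1.1% under TA is an assumption made here.

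**The plan's own figure.** The size of 72 concerns staple use only. With 63.3% (Introduction) and half of it, 31.65%, the unpooled formula gives (1.96 + 0.8416)² × (0.633 × 0.367 + 0.3165 × 0.6835) / 0.3165² = 35.15, so 36 per arm. The figure reproduces and is unaffected by this point.

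**Expected events**, same rate in both arms:
- 72 × 0.022 = 1.6 (0.8 per arm)
- 100 × 0.022 = 2.2 (1.1 per arm)

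**Chance of no event** at 2.2% versus 1.1%, (0.978 × 0.989)ⁿ with n per arm:
- n = 36: 0.301
- n = 50: 0.189

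The outcome is then constant, the residual variance is zero and the t statistic is undefined.

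**Least squares against Fisher, arm alone, k versus 0 events.** With n per arm, the difference is d = k/n, s² = k(1 − k/n)/(2n − 2), and t = d / √(2s²/n) on 2n − 2 degrees of freedom. For k = 4, n = 50: d = 0.08, s² = 3.68/98 = 0.03755, standard error 0.03876, t = 2.06, p = 0.042. Fisher's two-sided p is 2 × C(50,4)/C(100,4) = 2 × 230,300/3,921,225 = 0.117.

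| Events | n per arm | Least squares p | Uncorrected Chi-square p | Fisher p |
|---|---|---|---|---|
| 3 vs 0 | 36 | 0.079 | 0.077 | 0.239 |
| 3 vs 0 | 50 | 0.080 | 0.079 | 0.242 |
| 4 vs 0 | 36 | 0.040 | 0.040 | 0.115 |
| 4 vs 0 | 50 | 0.042 | 0.041 | 0.117 |
| 5 vs 0 | 36 | 0.020 | 0.020 | 0.054 |
| 5 vs 0 | 50 | 0.022 | 0.022 | 0.056 |
| 6 vs 0 | 36 | 0.010 | 0.011 | 0.025 |
| 6 vs 0 | 50 | 0.011 | 0.012 | 0.027 |

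**The adjusted model as planned.** Its p-value is not fixed by the event counts, so it was simulated at 4 versus 0 with 50 per arm. Assumed prevalences: hypertension 40%, diabetes 20%, dyslipidaemia 25%, postoperative TA 3%. Staple use was 63.3% in controls and 31.65% under TA.
- Covariates unrelated to the event: median p 0.060, 5th to 95th percentile 0.013 to 0.201, below 0.05 in about 42% of data sets.
- Half of the event patients given postoperative TA: median p 0.091, 5th to 95th percentile 0.012 to 0.501, below 0.05 in about 29%.

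The same 4 versus 0 result can thus give a p-value from about 0.01 to 0.5, depending on the covariates.

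**Type I error**, 2.2% in both arms, full enumeration for arm alone: least squares 0.7% (36 per arm) and 1.6% (50 per arm); Fisher 0.01% and 0.05%. Adjusted least squares, simulated under assumed prevalences: 1.3% and 1.7%.

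**The case against.** A reader might infer that the linear model produces false significance or an invalid p-value. The documents and the arithmetic do not support that.

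- **Error rate.** With events this rare, least squares rejects a true null in about 1-2% of trials, well under 5%. The table shows a disagreement with a very conservative exact test, not an inflated error rate.
- **Wrong model.** The 0.040 and 0.042 are for arm alone. Under the assumed prevalences, the planned adjusted model was not significant in most simulated 4 versus 0 data sets.
- **Not specific to regression.** The uncorrected Chi-square gives nearly the same p-values, so the contrast is between asymptotic and exact testing.
- **Unlikely counts.** At 2.2% versus 1.1%, exactly 4 versus 0 has a chance of C(n,4) × 0.022⁴ × 0.978ⁿ⁻⁴ × 0.989ⁿ: 0.5% with n = 36 and 1.1% with n = 50.

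All four stand, and they limit the claim. A linear model can also fit negative risks, but how often depends on covariate prevalences that the protocol does not give, so no weight is placed on it.

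Two limits of scope also stand. Section 10.1 assigns the regression to re-intervention only, not to the wider composite that includes transfusion. The Introduction's closing aim about postoperative haemorrhage is a separate matter: Section 2 already makes clip use the primary objective and Section 4.4 sizes the trial on it.

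None of this rescues the stated method. About two events cannot support six terms, two of the covariates lie downstream of treatment, and the protocol already names a suitable test in Section 10.2.

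**Conclusion.** The point holds as a wrongly stated method for a secondary outcome and should be fixed before analysis. It does not threaten the primary comparison or the sample size.

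The event counts assume that the centre's 2.2% rests on a definition close to that of Section 8.1.2 and that re-intervention here means re-intervention for haemorrhage, as in Section 2. A lower re-intervention rate would make the sparsity worse. The 30% and 19% chances of no event also assume a halved rate under TA. With no effect they are 0.978⁷² = 20% and 0.978¹⁰⁰ = 11%. The objection to staple use and postoperative TA as covariates needs no numerical assumption: both arise after randomisation.

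**What to change.** In Section 10.1, remove re-intervention from the sentence that extends the haemoglobin regression, together with its covariates. State instead that re-intervention within 30 days will be reported as counts per arm, the risk difference with an exact 95% confidence interval, and an unadjusted Fisher's exact test, all labelled descriptive.

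Name Fisher's test outright. The combined Chi-square and Fisher wording of Section 10.2 would leave the choice open, and at 4 versus 0 the two fall on opposite sides of 0.05. The descriptive label is warranted: the exact power of Fisher's test at 2.2% versus 1.1% is about 0.01% (36 per arm) or 0.05% (50 per arm).

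This reporting stays informative if no event occurs. The exact upper 97.5% limit for an arm with none is 1 − 0.025^(1/n): 9.7% for n = 36 and 7.1% for n = 50.

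The cost is a wording change, with no added patients, visits or data. The trial gives up a covariate-adjusted p-value that so few events could not support.

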## SUMMARY

**Rationale:** Fast-track protocols are frequently used in bariatric surgery and often include short-term thromboprophylaxis and short length of hospital stay. These treatment strategies may negatively affect the occurrence and diagnosis of postoperative hemorrhage. Over the years, the rates of venous thromboembolic events (VTE) decrease, while there seems to be an increase in the occurrence of postoperative hemorrhage. Tranexamic acid (TA) is a plasminogen inhibitor which inhibits fibrinolysis. Peroperative administration of TA may lower the incidence of postoperative hemorrhage.

**Objective:** This trial aims to investigate if peroperative administration of TA can reduce the peroperative and postoperative hemorrhage rates in laparoscopic sleeve gastrectomy.

**Study design:** This is a double-blind, single center randomized controlled trial.

**Study population:** Patients eligible for bariatric surgery according to the IFSO guidelines and undergoing a laparoscopic sleeve gastrectomy. Patients unwilling to give informed consent, patients with a medical history of bleeding or VTE and patients that use therapeutic anticoagulants will be excluded.

**Intervention (if applicable):** Patients are randomized between 2 groups: 1) Single dose of 1500 mg TA to be administered during induction of the procedure by anesthesiologist, and 2) Standard protocol with administration of placebo infusion.

**Main study parameters/endpoints:** Primary outcome measure is peroperative use of hemostatic clips. Secondary outcome measures are the decrease in hemoglobin after the procedure, rates of postoperative hemorrhage (i.e. hemorrhage needing administration of packed cells or a surgical or radiological re-intervention) and rates of VTE.

**Nature and extent of the burden and risks associated with participation, benefit and group relatedness:** All patients will be required to undergo one additional blood drawing in the week prior to the procedure which will be performed at their weighing appointment, meaning that this will not require an extra hospital visit. TA has very little side effects. Therefore we conclude that the expected benefits of the intervention outweigh the minor risks involved.

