## 2. OBJECTIVES

Primary Objective: Does the peroperative administration of TA lead to lesser use of peroperative extra hemostatic clips?

Secondary Objective(s): Does the peroperative administration of TA lead to a smaller hemoglobin decrease 1 day postoperatively and a lower reoperation rate within 30 days postoperative due to hemorrhage, or an increase in venous thromboembolic events within 3 months postoperative?

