### **10.3 Other study parameters**

Not applicable.

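### Section 10.1 compares re-interventions, but the declared secondary endpoint is haemorrhage needing packed cells or re-intervention, so bleeds treated by transfusion alone enter no stated comparison

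*Protocol*

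**What the plan says.** Section 8.1.2 lists among the secondary outcomes "rates of postoperative hemorrhage (i.e. hemorrhage needing administration of packed cells or a surgical or radiological re-intervention) within 30 days postoperative". The Summary gives the same composite without the window: "rates of postoperative hemorrhage (i.e. hemorrhage needing administration of packed cells or a surgical or radiological re-intervention) and rates of VTE".

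The secondary objective in section 2 is narrower and asks whether tranexamic acid leads to "a lower reoperation rate within 30 days postoperative due to hemorrhage".

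In the analysis section, 10.1 covers clip use and haemoglobin decrease and then continues: "These same analyses will be performed to assess the differences in amount of patients needing to undergo a" re-intervention, with postoperative tranexamic acid added as a covariate. Section 10.2 covers "Differences in rates of DVT (yes/no), PE (yes/no) and in rates of administration of postoperative tranexamic acid (yes/no) between the 2 groups". Section 10.3, for other parameters, reads "Not applicable".

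Section 8.3 states that packed cells and postoperative haemorrhage are both taken from the electronic patient file.

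**The concern.** An endpoint and its analysis should count the same event. Here the endpoint section counts a patient who bleeds and is only transfused, while the analysis section and the objective do not. A statistician who follows section 10 literally would report a comparison for an event other than the declared one, and none for the declared one.

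Postoperative haemorrhage is also the clinical reason for the trial. The Introduction closes by giving its reduction as the aim, and sections 11.4 and 13.2 set the expected reduction against the risks to participants. Three wordings for that outcome leave open, until the data are in, which haemorrhage count is reported.

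**Working it through.** **1. The wordings side by side**

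| Place | Packed cells alone | Surgical re-intervention | Radiological re-intervention | Cause: haemorrhage | 30-day window |
|---|---|---|---|---|---|
| Summary | counts | counts | counts | stated | not stated |
| 8.1.2 | counts | counts | counts | stated | stated |
| 2 | does not count | counts | not naturally covered by reoperation | stated | stated |
| 10.1 | does not count | counts | counts | not restated | not restated |
| 10.2, 10.3 | no haemorrhage outcome | – | – | – | – |

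The transfusion-only column is the firm part of the point: such a patient is an event under 8.1.2 and the Summary, and not under section 2 or 10.1. The two right-hand columns show a gap in the wording of 10.1 only.

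**2. The plan's own figure**

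The only sample size calculation (section 4.4) is for clip use. With 63.3% from the Introduction and a 50% relative decrease to 31.65%, two-sided 5% and 80% power, the unpooled normal formula gives

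n = (1.960 + 0.842)² × (0.633 × 0.367 + 0.3165 × 0.6835) / 0.3165² = 35.15, so 36 per arm and 72 in total.

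This reproduces the stated figure and has no bearing on haemorrhage, for which the protocol gives no calculation.

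**3. How many haemorrhages to expect**

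Inputs: 2.2% after sleeve gastrectomy at this centre (Introduction); 72 patients (section 4.4) or 100 patients (section 3).

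- No effect of tranexamic acid: 72 × 0.022 = 1.58; 100 × 0.022 = 2.20.
- Rate halved in the active arm (assumption): 36 × 0.022 + 36 × 0.011 = 1.19; 50 × 0.022 + 50 × 0.011 = 1.65.

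**4. Could the definition change an inference?**

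Two-sided Fisher's exact test, all events in one arm:

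| Split | 36 per arm | 50 per arm |
|---|---|---|
| 3 vs 0 | 0.239 | 0.242 |
| 5 vs 0 | 0.054 | 0.056 |
| 6 vs 0 | 0.025 | 0.027 |

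At least 6 vs 0 is needed for p < 0.05. At 2.2%, the chance of 6 or more events in one arm is 0.0001 (36 patients) or 0.0008 (50 patients). Moving one patient in or out of the count changes the table, not a significance decision.

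**5. How likely is a lost event?**

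The protocol does not say what share f of haemorrhages is managed with packed cells alone, so f is an assumption. The chance that at least one patient meets 8.1.2 but not 10.1 is 1 − (1 − 0.022 f)^N:

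| f (assumed) | N = 72 | N = 100 |
|---|---|---|
| 0.25 | 0.33 | 0.42 |
| 0.50 | 0.55 | 0.67 |
| 0.75 | 0.70 | 0.81 |

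These figures take 2.2% in both arms. They also treat that rate as if it used the 8.1.2 definition, which the Introduction does not say. They show that a lost event is plausible and no more.

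**The case against.** The best defence is that there is one definition and two loose paraphrases of it. The Summary and 8.1.2 agree. Section 8.3 collects haemorrhage as an item in its own right, and the opening of section 10 mentions unregistered packed cells as a source of missing data, so their use seems to be foreseen. A statistical analysis plan, not shown here, may name the composite. This explains what was probably meant, but it does not remove the mismatch: 10.1 does not leave the outcome open, it names a different one. What stands is that the absence of a comparison can be asserted only for this protocol as written.

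A reader might also infer that 10.1 sets out to count re-interventions for any reason. The documents do not support that. Section 2 and 8.1.2 both give haemorrhage as the cause and 30 days as the window, and section 11.4 speaks of re-interventions as a consequence of bleeding. The covariate in 10.1, postoperative tranexamic acid, is described in the Introduction as given for suspected bleeding. Entry of other re-interventions is a risk of the literal wording, not a stated intention, and the protocol gives no rate from which to size it.

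A third objection is that with about two events nothing can be concluded anyway. That is right about inference, and it limits the severity. It does not make the event definition unimportant, because with so few events the count by arm is the result that will be reported.

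**Conclusion.** The point holds as an inconsistency within the protocol. Sections 2, 8.1.2 and 10.1 name three different events for one secondary outcome. As written, section 10 contains no between-arm comparison of the 8.1.2 composite, and bleeds treated with packed cells alone drop out although the data are collected.

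Its size is modest. About 1.6 to 2.2 haemorrhages are expected if tranexamic acid has no effect, and fewer if it works, so the comparison is descriptive under any of the definitions. It would be tempting to say that one patient classified differently changes the result. That is true of the reported count and not of any test, since 6 vs 0 events would be needed. The primary endpoint and the sample size are unaffected.

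The textual finding rests on no assumption. The expected counts rest on the 2.2% rate applying to trial patients, and the chance of a lost event rests on an assumed transfusion-only share. This should be fixed, but it is not critical to the trial.

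**What to change.** - In section 10, replace re-intervention with the 8.1.2 endpoint: haemorrhage within 30 days that needs packed cells or a surgical or radiological re-intervention. State that a re-intervention counts only when its recorded indication is haemorrhage.
- Compare this by randomised arm as a single yes/no outcome. Fisher's exact test, already named in section 10.2, suits so few events.
- List packed cells, surgical re-intervention and radiological re-intervention descriptively by arm.
- Align section 2 with 8.1.2, and add the 30-day window to the Summary.

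The cost is a few sentences in the Summary and sections 2 and 10. If the case report form, which is not shown, does not already record why a re-intervention was done, one data item is needed. No extra patients, visits or procedures are required.

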### **10.2 Secondary study parameter(s)**

Differences in rates of DVT (yes/no), PE (yes/no) and in rates of administration of postoperative tranexamic acid (yes/no) between the 2 groups will be calculated using Chi-Square (Fisher's Exact) tests.

### **10.3 Other study parameters**

Not applicable.

### **10.4 Interim analysis (if applicable)**

Not applicable.

## **11. ETHICAL CONSIDERATIONS**

### **11.1 Regulation statement**

The study will be conducted according to the principles of the Declaration of Helsinki (version 10, October 2013) and in accordance with the Medical Research Involving Human Subjects Act (WMO).

